Aim 3. To determine implementation costs and cost-effectiveness of screening and BHS-delivered intervention. Costs will be obtained as described in **C.8.c.** We will assess the incremental cost-effectiveness ratio as the additional cost per unit of outcome (e.g., 1% increase in mean ART adherence) between the observation and intervention phases. For example, if the BHS-delivered intervention costs \$100 more per patient than during the observational phase and increases mean ART adherence from 85% to 90%, then the intervention costs \$2000 per additional unit of adherence. A cost-effectiveness acceptability curve will be obtained from the distribution of the ICER which will be constructed using the bootstrap method based on the variances of estimates of costs and effectiveness as we have done in prior work.¹⁶⁶ This can be used by policy-makers to determine potential gain in effectiveness for acceptable cost thresholds.

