**TITLE:**

Computerized Substance Use and Depression Screening and Behavioral Treatment in HIV Primary Care

NCT NUMBER:

NCT03217058

VERSION DATE:

October 5, 2022

Research Question: What are the key barriers to implementation, factors associated with effectiveness, and cost of tablet-based screening for the continuum of SUD severity and depression, followed by BHS-delivered interventions for those who screen positive.

Aim 1. To evaluate the implementation of computerized SUD and depression screening and BHS-delivered intervention in HIV primary care.

Hypothesis 1: SUD and depression screening rates and BHS-delivered intervention will be higher in the intervention phase compared with the observation phase and will be maintained long-term.

Hypothesis 2: Greater HIV severity and younger age will increase screening rates for SUD and depression.

Hypothesis 3: More BHS-delivered intervention will occur with higher HIV, SUD and/or depression severity.

Aim 2. To examine the effectiveness of computerized screening and BHS-delivered intervention in HIV primary care among patients with moderate or high SUD risk or depression severity.

Hypothesis 1: SUD and/or psychiatry specialty care treatment initiation and antidepressant prescription use will be greater in the intervention phase compared with the observation phase.

Hypothesis 2: HIV outcomes, including ART adherence, HIV RNA control, VACS index score, and retention in HIV care will be improved in the intervention phase compared with observation phase.

Hypothesis 3: SUD and depression symptoms will decrease after implementation of the intervention.

Aim 3. To determine implementation costs and cost-effectiveness of screening and BHS-delivered intervention.

We will measure the cost per patient screened, and among those screening positive, the cost per patient initiating BHS-delivered intervention. We will also evaluate the cost-effectiveness of the intervention for achieving improvements in each HIV, SUD and depression outcome.

Aim 4: Perform key informant interviews to evaluate provider- and clinic-level implementation barriers and facilitators to computerized screening and BHS-delivered intervention.

Semi-structured interviews for selected providers and clinic staff, including qualitative and quantitative components, will be performed in each clinic.

Study Design

Description of Study Phases

Phase 1: Data only

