Patients will only be flagged to be asked to complete the questionnaire every 6 months. Clinicians may choose to administer the questionnaire via the suspended hyperspace feature in the interim period if they deem it appropriate follow up for clinical care, however no appointment will be flagged to have a questionnaire directly attached for patient completion prior to their visit if a TAPS/AOQ has been completed within 6 months.

BHS-delivered intervention. Drs. [name] and [name] will meet with clinic BHSs to introduce (or review) core cognitive behavioral therapy (CBT) - and motivational interviewing (MI)-based interventions. BHSs will be trained to review results of all computerized screenings and to provide outreach by phone²¹⁰ and/or web-based patient portal (KP.org) using secure messages. They will be coached on patient engagement and patient-centered goal setting (e.g., noting screening results but also focusing on patients' priorities and concerns), and instructed to offer individual MI/CBT sessions by phone or in person, according to clinical assessment and patient preference. MI and CBT can be effectively combined to address co-occurring depression and substance problems.²¹⁷⁻²¹⁹ BHSs will use MI to enhance motivation to initiate specialty SUD or psychiatry treatment within KPNC for higher severity patients, which is available for all members in facilities nearby to each primary care clinic.

Intervention training. The study team will meet with staff and providers early in the implementation phase to assist with planning for tablet or suspended hyperspace-based administration based on our prior work, e.g., work flow considerations.⁹¹ Orientation for physicians and other providers (e.g., nurse practitioners) will include review of the new screening measures, how to locate scores in the EHR, and the BHS role in patient care and the intervention.

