BHSs are Masters or Doctoral-level psychologists or licensed clinical social workers with a training foundation and experience in behavioral interventions. Currently they provide care across medical centers; and our study will support their time dedicated to HIV clinics. They often co-manage patients' medical conditions through non-pharmacologic and behavioral interventions, collaborate with primary care providers, and provide consultation to other team members in the areas of mental health, behavioral medicine, and health psychology. [name] will provide BHSs training on MI and CBT for depression and substance-use problems. Training will include 15 hours of instruction and supervised practice of brief, solution-focused, MI/CBT interventions involving 3 training cases (volunteer actors posing as patients), which is consistent with the average number of hours required for training in past clinical trials.⁹⁵

The initial training with BHSs will also include new technology and workflow (e.g., accessing screening data and documenting encounters in the EHR), and guidelines for when to help patients initiate specialty SUD and psychiatry care (i.e., for high severity patients), suicide risk assessment, and follow-up (monitoring patient engagement and following up as needed with patient and care team to ensure linkage to treatment). Monthly consultation with Drs. [name] and [name] will reinforce key clinical skills, enable clinicians to share case material and obtain feedback, and troubleshoot system and workflow challenges.

Study Timeline. This study has a 5-year timeline (**Table 2**). This will be sufficient for observation and follow-up of 4600 patients, data extraction and analysis, and interpretation and dissemination of results.

Study Activities	Year 1	Year 2	Year 3	Year 4	Year 5
Study start up activities					
Clinic 1 implementation					
Clinic 2 implementation					
Clinic 3 implementation					
Ongoing BHS support and coaching					
Semi-structured clinician interviews					
One year clinic data follow up period					
Data analysis					
Manuscript Preparation					
Dissemination activities					

Data Sources. Study measures will be obtained from the EHR, HIV Registry, and informant interviews.

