KPNC EHR. The EHR databases links information using unique member identifiers from multiple data sources including demographics, membership, ambulatory, inpatient, laboratory and prescription data. Unit costs of services obtained for each patient encounter and service are also available and can be calculated by member over time, or aggregated to physician or facility level. Vital status is captured comprehensively from member proxy reporting, deaths during a KP hospitalization, regional cancer registry vital status, quarterly Social Security Administration vital status files and death certificates. Additional detail on all EHR data sources is provided in KPNC Resources. After implementation of the intervention, results of KP.org-, tablet-, and suspended hyperspace-based SUD and depression screening during routine primary care visits will be added to the EHR. **HIV registry.** The HIV registry includes all HIV patients since the early 1980s, with HIV-infection confirmed by chart review. It maintains up-to-date lists of all HIV patients, HIV transmission risk factors, dates of known HIV infection, AIDS diagnoses, and complete HIV-related lab and pharmacy data. A total of 8,186 HIV patients are current KPNC members, including 4,600 (56% of all KPNC HIV patients) from the three study clinics.

Study Measures. We will include relevant patient demographic factors in all analyses, including age, sex, race/ethnicity, and HIV risk group. Evaluating these demographics in the context of an insured population allow for the evaluation of potential disparities in screening and treatment rates, independent of differences in access to care. Other study measures for each study Aim are described below.

Aim 1 measures (implementation)

- **SUD and depression screening** during the observational phase will include EHR-based provider-documented screening for SUDs and depression. Intervention phase screening will include provider-documented screening and KP.org-, tablet-, and suspended hyperspace-based screens, also in the EHR.
- **BHS-delivered intervention** during the observational and intervention phases will be defined as one or more in-person or phone visits with a BHS. We will also measure the number of phone and in-person visits.

Aim 2 measures (effectiveness)

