- **SUD and depression treatment initiation.** Patients scoring in the high SUD risk level on the TAPS or moderate to severe depression on the PHQ-9 will be encouraged to initiate specialty SUD or psychiatry treatment, and the BHS will use MI to help enhance motivation to initiate care. We will analyze SUD and depression treatment initiation rates using electronic administrative data; that is, whether the patient attended at least one in-person or phone visit with a BHS and/or in SUD or psychiatry treatment.
- **Antidepressant prescription rates.** Any prescription for antidepressants, including standard medications based on best practices guidelines in the treatment of depression.^{211,230}
- **Antiretroviral (ART) medication adherence.** ART adherence will be defined using the Medication Possession Ratio (MPR)^{234,235} for each ART prescribed.²³⁶ MPR is calculated using a numerator of days' supply dispensed from first fill to end of the interval (i.e., 12 months), and a denominator of total days between first fill to end of the interval, with values ranging from 0% to 100%. Mean refill adherence will be calculated across all individual ARTs dispensed in the interval²³⁷ distinguishing between true non-adherence or a change in ART (i.e., a new ART medication prescribed within 30 days) as in our previous work.^{238 179}
- **HIV RNA response.** HIV RNA control, defined as undetectable HIV RNA levels below 75 copies/ml.
- **Retention in care.** We will use the Institute of Medicine's encounter-based definition of retention, defined as ≥ 2 HIV primary care visits within a 12-month period, ≥ 90 days apart.¹⁵⁵
- **VACS index score.** The VACS score has been shown to correlate with mortality.¹⁸⁶ It incorporates 7 routinely collected clinical variables, including age, CD4, HIV RNA, hemoglobin, fibrosis index 4 (FIB-4), Hepatitis C, and

estimated glomerular filtration rate. The FIB-4 index incorporates age, platelets, and two liver function test results, including aspartate aminotransferase and alanine aminotransferase.

- **TAPS (SUD risk level) and PHQ-9 (Depression).** See section **C.6.b.**

Data Analysis

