Aim 2. To examine the effectiveness of computerized screening and BHS-delivered intervention in HIV primary care among patients with moderate or high SUD risk or depression severity. We will first compare treatment initiation in specialty clinic for those with severe SUD or depression problems and anti-depression medication prescription rates, among all patients who screen positive (**Aim 2, Hypothesis 1**). The repeated cross-section analyses will be conducted using the random effects (mixed) model framework as above with the dependent variable (whether a patient received any prescription orders initiation with SUD specialty care or Psychiatry treatment for their SUD (depression) being dichotomous. Drawing from preliminary analyses, we will include all patient-level predictors (e.g. demographics such as age and gender, severity) that are likely to be related to these outcomes. These models will use logistic regression since the outcome is dichotomous. We will use the SAS® NL MIXED or similar procedure for analyses. Sample size permitting, we will also examine the use of Buprenorphine/Naloxone for the subset of HIV patients with opioid addiction.^{243,244}

We will also examine the longitudinal (cohort) effect of the intervention on clinical outcomes by comparing changes in HIV clinical parameters (**Aim 2, Hypothesis 2**) and SUD and depression severity (**Aim 2, Hypothesis 3**) for those who have return visits within the study observation period, adjusting for time between visits. We will examine changes in these values between the patient's initial screening and their subsequent visits using the random effects model described above. For example, we expect the coefficient of interest of the time x intervention variable to be positive, which would imply that BHS-delivered intervention results in greater increase in ART adherence.

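### The Aim 2 treatment-initiation measure counts a BHS visit alone, while Hypothesis 1 and its analysis concern SUD or psychiatry specialty care

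*Protocol*

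**What the plan says.** The protocol describes treatment initiation in three places that bear on the same hypothesis.

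- **Aim 2, Hypothesis 1** (opening list of aims): "SUD and/or psychiatry specialty care treatment initiation and antidepressant prescription use will be greater in the intervention phase compared with the observation phase".
- **Study Measures, Aim 2 measures (effectiveness)**: the outcome is "whether the patient attended at least one in-person or phone visit with a BHS and/or in SUD or psychiatry treatment". The sentence before it says that patients at high SUD risk or with moderate to severe depression "will be encouraged to initiate specialty SUD or psychiatry treatment, and the BHS will use MI to help enhance motivation to initiate care".
- **Data Analysis, Aim 2**, citing Hypothesis 1: the plan is to "compare treatment initiation in specialty clinic for those with severe SUD or depression problems", and the model's dependent variable includes "initiation with SUD specialty care or Psychiatry treatment for their SUD (depression) being dichotomous".

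Three other places show what a BHS visit is in this study. Under Aim 1 measures (implementation), receipt of the BHS-delivered intervention "will be defined as one or more in-person or phone visits with a BHS". The description of the intervention says "BHSs will use MI to enhance motivation to initiate specialty SUD or psychiatry treatment within KPNC for higher severity patients". The Intervention training text says of the BHSs: "Currently they provide care across medical centers; and our study will support their time dedicated to HIV clinics".

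**The concern.** The hypothesis and the analysis text ask whether more patients reach specialty care. The measure asks whether they reach specialty care or the BHS. Because of the and/or, one BHS phone call is enough.

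That call is also the event by which Aim 1 records that the intervention was delivered. Aim 1 Hypothesis 1 expects it to be more frequent in the intervention phase, and the study pays for the BHS time that makes it so. Under the measure as written, delivering the intervention counts as evidence that the intervention works. The Aim 2 comparison could then largely repeat an Aim 1 result.

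An analyst could code either variable and claim to follow the protocol. The choice can decide whether this part of Hypothesis 1 is reported as met. Antidepressant prescribing, which is a separate measure, and Hypotheses 2 and 3 are not affected.

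**Working it through.** **The texts side by side**

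| Place in the protocol | What counts | Does a BHS visit alone count? |
|---|---|---|
| Aim 2, Hypothesis 1 | SUD and/or psychiatry specialty care (plus antidepressant use) | No |
| Data Analysis, Aim 2 | Initiation in a specialty clinic (plus prescriptions) | No |
| Aim 2 measures (effectiveness) | BHS visit and/or SUD or psychiatry treatment | Yes |
| Aim 1 measures (implementation) | BHS visit, as receipt of the intervention | It is the intervention |

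Nothing in the protocol reconciles the third row with the first two.

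**Size of the possible effect**

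The protocol states no rate, effect size or sample size for this outcome, so there is no figure of its own to reproduce. Every rate below is an assumption. Let *s* be the proportion starting specialty care, held equal in both phases so that the true effect on specialty care is zero. Let *b* be the proportion with at least one BHS visit. The overlap pattern is taken to be the same in both phases.

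- Independence: combined = 1 − (1 − *s*)(1 − *b*), so the gain is (1 − *s*)(*b*₁ − *b*₀).
- Complete overlap (the smaller group lies inside the larger): combined = max(*s*, *b*).

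With *s* = 10%:

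| BHS contact, observation to intervention | Combined, independence | Combined, complete overlap | Specialty only |
|---|---|---|---|
| 0% to 40% | 10% to 46% | 10% to 40% | 10% to 10% |
| 10% to 40% | 19% to 46% | 10% to 40% | 10% to 10% |
| 20% to 40% | 28% to 46% | 20% to 40% | 10% to 10% |
| 0% to 10% | 10% to 19% | 10% to 10% | 10% to 10% |

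For example, in the second row, 1 − 0.90 × 0.90 = 0.19 and 1 − 0.90 × 0.60 = 0.46.

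Now let *s* run from 5% to 20% and baseline BHS contact from 0% to 20%, with a rise to 40%:

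- Independence: from 0.80 × 0.20 = 16 points (*s* = 20%, baseline 20%) to 0.95 × 0.40 = 38 points (*s* = 5%, baseline 0%).
- Complete overlap: from 40 − 20 = 20 points to 40 − 5 = 35 points.
- If baseline contact is restricted to 10% to 20%: 16 to 28.5 points under independence (0.95 × 0.30 = 0.285) and 20 to 30 points under complete overlap.

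A second set of assumed rates gives the same picture under independence. With *s* = 20% and BHS contact going from 2% to 10%, the combined measure goes from 21.6% to 28.0%, a gain of 6.4 points. With *s* = 5% and BHS contact going from 10% to 50%, it goes from 14.5% to 52.5%, a gain of 38 points.

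**The case against.** The best case for the measure is that the BHS treats patients as well as referring them. The protocol has BHSs trained in motivational interviewing and cognitive behavioral therapy, and offering individual sessions. The role of moving patients on to specialty care is tied to those with higher severity. The measure's heading speaks of treatment initiation in general, and the sentence before the definition describes what patients are encouraged to do without defining the outcome. This stands: counting BHS care as treatment is not wrong in itself, and the lead-in is only supporting evidence. It does not bring the measure into line with the hypothesis or the analysis text.

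The sentence giving the dependent variable is also garbled. It runs prescription orders and specialty initiation together, so it is a weak anchor. That is fair, but the sentence before it speaks plainly of initiation in a specialty clinic, and Hypothesis 1 is equally clear.

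The rates are invented, and the largest gains need a 0% baseline. That fits poorly with BHSs already working in the medical centers and with BHS visits being measured in the observational phase as well. This too stands, and it is why the narrower range for a 10% to 20% baseline is shown.

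Finally, the hypothesis and analysis text have a good claim to govern, and BHS visits are recorded separately, so the components could be separated later. But the protocol does not say which text governs, and the measure is where the outcome is operationally defined.

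**Conclusion.** The concern holds. The protocol fixes two incompatible outcomes for the treatment-initiation part of Aim 2 Hypothesis 1. This is a contradiction in the text and not a detail left to a statistical analysis plan. If the hypothesis and analysis text are followed, no problem arises. If the measure is followed, a rise in BHS contacts alone can make this part of the hypothesis appear met.

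The upward direction follows from the expected rise in BHS visits, given unchanged specialty use and a similar overlap in both phases. The size does not follow from the text. Under the assumed rates with a rise to 40% contact, it is 16 to 38 points under independence and 20 to 35 under complete overlap. It is zero if overlap is complete and BHS use does not exceed specialty use. The matter should be fixed, but it is confined to one component of one hypothesis.

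**What to change.** Amend the treatment-initiation item under Aim 2 measures (effectiveness) so that the outcome judging Hypothesis 1 is at least one visit, by phone or in person, to SUD specialty care or psychiatry. Report BHS visits under Aim 1, where they are already defined. If the combined measure is kept, present it as a separate descriptive outcome, split into BHS only, specialty only, and both.

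It would be sensible at the same time to reword the dependent-variable sentence in the Aim 2 analysis so that prescriptions and specialty initiation read as two outcomes.

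The cost is a wording change. The visits already come from electronic administrative data, so nothing new is collected. Reported initiation rates will be no higher, and usually lower, than under the combined measure.

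### SUD and depression treatment initiation is defined by one any-service visit rule not tied to the condition screened positive, and the Aim 2 hypothesis and analysis text word the outcome differently

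*Protocol*

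**What the plan says.** Four places in the protocol bear on this outcome.

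- **Aims, Aim 2 Hypothesis 1:** "SUD and/or psychiatry specialty care treatment initiation and antidepressant prescription use will be greater in the intervention phase compared with the observation phase". The outcome is specialty care of either kind. BHS visits are not named.
- **Study Measures, Aim 2 measures (effectiveness):** "We will analyze SUD and depression treatment initiation rates using electronic administrative data". The operational rule follows at once: "whether the patient attended at least one in-person or phone visit with a BHS and/or in SUD or psychiatry treatment". The patients concerned are described as one group: "Patients scoring in the high SUD risk level on the TAPS or moderate to severe depression on the PHQ-9 will be encouraged to initiate specialty" care in SUD or psychiatry.
- **Data Analysis, Aim 2:** "We will first compare treatment initiation in specialty clinic for those with severe SUD or depression problems". The dichotomous dependent variable is given as "initiation with SUD specialty care or Psychiatry treatment for their SUD (depression) being dichotomous".
- **Study Measures, Aim 1 measures (implementation):** BHS-delivered intervention "will be defined as one or more in-person or phone visits with a BHS". A BHS visit is therefore already the Aim 1 delivery measure.

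**The concern.** The measures section speaks of rates in the plural, one for SUD and one for depression, but supplies a single yes/no rule that returns the same value for both. The analysis text suggests care given for the patient's own condition. The hypothesis asks about either specialty. Two analysts working from different sections would code the same record differently.

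At stake is what a phase difference in this outcome would mean. SUD programs and psychiatry are different services and may respond differently to screening and BHS outreach. A yes/no that accepts either one, or a BHS visit, cannot say which of them moved. A change in SUD care can be diluted by steady psychiatry use. A change in psychiatry or BHS use can also be credited to SUD care that did not change.

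**Working it through.** **Step 1. Apply each wording to the same records.** Take patients in the analysis with exactly one qualifying contact.

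| Record | Measures section, literal | Analysis text, read as condition-matched | Hypothesis 1, either specialty |
|---|---|---|---|
| SUD-positive only, one psychiatry visit | initiated | not initiated, unless the visit was for SUD | initiated |
| Depression-positive only, one SUD-program visit | initiated | not initiated, unless the visit was for depression | initiated |
| Positive for both, one psychiatry visit | initiated | initiated for depression; not for SUD unless the visit was for SUD | initiated |
| Positive for either, one BHS visit only | initiated | not initiated | not initiated |

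The three wordings disagree on every row. The first three rows turn on matching service to condition, and the fourth on whether a BHS visit counts.

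**Step 2. Look for a plan figure to reproduce.** There is none. The protocol gives no initiation rate, no number screening positive and no power statement for this outcome. Everything below is illustrative.

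**Step 3. See what the literal rule does among SUD-positive patients.** Let s, q and b be the proportions with a SUD specialty, psychiatry and BHS visit, assumed independent. The composite is 1 − (1 − s)(1 − q)(1 − b). All rates are assumptions.

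*Dilution* (s from 10% to 18%, a true change of 8.0 points; q unchanged; b = 0):

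| q | Composite before | Composite after | Change |
|---|---|---|---|
| 10% | 1 − 0.90×0.90 = 19.0% | 1 − 0.82×0.90 = 26.2% | 7.2 points |
| 20% | 1 − 0.90×0.80 = 28.0% | 1 − 0.82×0.80 = 34.4% | 6.4 points |
| 30% | 1 − 0.90×0.70 = 37.0% | 1 − 0.82×0.70 = 42.6% | 5.6 points |
| 40% | 1 − 0.90×0.60 = 46.0% | 1 − 0.82×0.60 = 50.8% | 4.8 points |

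*False credit from psychiatry* (s fixed at 10%, q from 20% to 30%, b = 0): 28.0% to 1 − 0.90×0.70 = 37.0%, a gain of 9.0 points with no change in SUD care.

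*False credit from BHS visits* (s = 10%, q = 20%, both fixed; b from 5%): the starting value is 1 − 0.90×0.80×0.95 = 31.6%. With b at 20%, 30% or 50% the composite is 42.4%, 49.6% or 64.0%, a gain of 10.8, 18.0 or 32.4 points.

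*Both specialties rise* (s from 10% to 18%, q from 20% to 30%, b = 0): 28.0% to 1 − 0.82×0.70 = 42.6%, a gain of 14.6 points, larger than either component's own change.

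**Step 4. Ask whether the composite can be unpicked.** A move from 28.0% to 37.0% arises when psychiatry rises from 20% to 30% with SUD care flat at 10%. It also arises with psychiatry flat at 20% and SUD care rising to 1 − 0.63/0.80 = 21.25%. The result is the same, and in one case SUD care did not change while in the other it more than doubled.

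**The case against.** The strongest reply is that the analysis text already matches service to condition. On that reading its parenthesis means respectively: one model for SUD and a parallel one for depression. The plural rates in the measures section fit this. The reading is reasonable, and it rules out saying that the protocol has settled that a psychiatry visit equals SUD treatment. It does not remove the problem. The sentence is garbled, it does not exclude psychiatry visits for SUD, and the only explicit operational definition says something else.

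Second, Hypothesis 1 is worded with and/or, so an either-specialty outcome tests what is hypothesised. That stands, and it is why the composite should be kept. It does not deliver the separate rates the measures section promises, and the literal rule adds BHS visits that the hypothesis does not name.

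Third, a reader might infer that a real change in SUD care is masked. The documents do not support that. Masking needs psychiatry use to stay flat and BHS visits to be left out. The BHS-delivered intervention section has the BHS promoting both SUD and psychiatry treatment, and BHS contact is what the intervention supplies. The literal composite could well rise, and the error can run either way.

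Fourth, derivation detail can be left to a SAP, which is not shown. That would answer silence. Here the protocol states a derivation, and its own sections conflict.

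Fifth, matching needs condition-specific positive status in both phases, and the protocol says that screening for substances other than alcohol and tobacco is not standardized in the observational phase. This is a genuine limit on comparability. It applies equally to the planned analysis, which already restricts to patients who screen positive.

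**Conclusion.** The point holds as a conflict between the Aim 2 hypothesis, the measures definition and the analysis text. Followed literally, the definition credits any of three services whatever the patient screened positive for. It therefore cannot show whether SUD care or depression care changed. This follows from the wording and needs no assumed rate.

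The size is not known. With assumed rates and independent components, an 8.0-point SUD change appears as 4.8 to 7.2 points when psychiatry is steady at 10% to 40%. Apparent gains of 9.0 points (psychiatry) or 10.8 to 32.4 points (BHS visits) arise with no SUD change. These figures show direction and possibility only. They do not establish that an effect will be hidden or invented in this trial, and Hypothesis 1 as worded can still be tested.

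**What to change.** Reconcile Aim 2 Hypothesis 1, the Aim 2 measures section and the Aim 2 analysis text around one set of definitions:

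1. **SUD initiation:** at least one SUD specialty visit, or a psychiatry visit carrying a SUD diagnosis, among SUD-positive patients.
2. **Depression initiation:** at least one psychiatry visit, among depression-positive patients.
3. **Patients positive for both** enter both analyses and are scored separately in each.
4. **Either-specialty composite:** keep it as the direct test of Hypothesis 1, reported beside the two matched outcomes.
5. **BHS visits:** state explicitly whether they count toward any initiation outcome. Reporting them separately would agree with the hypothesis and the analysis text, and they are already measured under Aim 1.

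Each matched outcome can use the random effects logistic model already planned. The cost is recoding visits by department and diagnosis from data the study already extracts, and fitting two models where one might have served. The downsides are small: some added multiplicity, and dual-diagnosis care in psychiatry without a coded SUD diagnosis is credited only to depression. The uneven ascertainment of SUD in the observational phase remains and should be acknowledged when the SUD outcome is reported.
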